#### **7.1.1.7. Eye-related Symptom Assessment**

The subjects will be asked about eye-related symptoms at Screening and with all subsequent physical exams while on treatment.

If there are any eye-related symptoms of severity Grade  $\geq 2$  at Screening or if the subjects develop any eye-related symptoms of severity Grade  $\geq 2$  while on study treatment, an ophthalmologic evaluation/consult must be performed and the outcome must be reported on the ophthalmologic eCRF.

#### **7.1.1.8. ECOG**

The ECOG performance index is provided in Appendix B.

#### **7.1.1.9. Vital Signs**

Vital signs will include blood pressure, heart rate, respiratory rate and body temperature and will be assessed after the subject has been resting in the sitting position for at least 3 minutes.

#### **7.1.1.10. Patient-Reported Outcomes**

The PRO instrument, EQ-5D-5L (Appendix E), will be administered in this study. These questionnaires are to be completed by the subject prior to any other study procedures at that visit.

The EQ-5D-5L is a standardized instrument used to measure of health outcome (EuroQol Group 1990) and consists of a 5-item questionnaire and a “thermometer” visual analogue scale ranging from 0 (worst imaginable health state) to 100 (best imaginable health state). The scores for the 5 dimensions are used to compute a single utility score ranging from 0 to 1, representing the general health status of the individual. The 5 dimensions evaluated are mobility, self-care, usual activities, pain/discomfort, and anxiety/depression.

**7.1.1.11. Cumulative Illness Rating Scale (CIRS)**

The CIRS is a measure of comorbid medical conditions. As an individual ages, the number of comorbid medical conditions increases, which can impact treatment tolerance to anti-cancer therapy (Welch 1996). The scoring sheet for CIRS is found in Appendix F.

**7.1.1.12. Medical Resources Usage (MRU)**

Hospitalizations, emergency department visits, blood product transfusions, and hematopoietic growth factor use will be collected for each treatment arm.

**7.1.1.13. Study Drug Compliance Review**

Study drug compliance review includes subject instruction and routine review of study drug diary and evaluation of contents of study drug containers from home administration.

**7.1.2. Laboratory****7.1.2.1. Hematology**

Hematology parameters will include a complete blood count: white blood cells, red blood cells, hemoglobin, hematocrit, platelets, neutrophils, lymphocytes, monocytes, eosinophils, basophils and bands (if reported).

**7.1.2.2. Chemistry (Serum)**

Serum chemistry parameters will include sodium, potassium, chloride, blood urea nitrogen (BUN), creatinine, glucose, calcium, total protein, albumin, AST, ALT, alkaline phosphatase, total bilirubin, lactate dehydrogenase (LDH), phosphate, uric acid, magnesium and bicarbonate. Creatinine clearance (Cockcroft-Gault) will be calculated with every serum chemistry.

**7.1.2.3. Coagulation Panel**

Measurement of prothrombin time (PT)/INR, and activated partial thromboplastin time (aPTT) will be performed at Screening.

**7.1.2.4. Hepatitis Serologies**

Hepatitis serologies include hepatitis B surface antigen, hepatitis B surface antibody, hepatitis B core antibody, and hepatitis C antibody, and will be evaluated by central laboratory. Subjects who are positive for hepatitis B core antibody, hepatitis B surface antigen, or hepatitis C antibody must have a negative PCR result before enrollment. Those who are PCR positive will be excluded.

### 7.1.2.5. Pregnancy Test

Serum pregnancy test will be performed centrally at Screening only for women of reproductive potential. A urine pregnancy test will also be performed on Day 1 prior to first dose. If positive, pregnancy must be ruled out by ultrasound to be eligible. This test may be performed more frequently if required by local regulatory authorities.

### 7.1.3. Diagnostics/Procedures

#### 7.1.3.1. ECG

Subjects should be in supine position and resting for at least 10 minutes before study-related ECGs. During visits in which both ECGs and blood draws are performed, it is recommended that ECGs are performed first.

At Screening, 12-lead ECGs will be done *in triplicate* ( $\geq 1$  minute apart).

Abnormalities noted at Screening should be included in the medical history.

ECGs should be performed at the investigator's discretion, particularly in subjects with arrhythmic symptoms (eg, palpitations, lightheadedness) or new onset of dyspnea.

#### 7.1.3.2. CT/MRI

CT scans of the neck, chest, abdomen and pelvis will be performed throughout the study until disease progression is confirmed. MRI may be used to evaluate sites of disease that cannot be adequately imaged using CT (in cases where MRI is desirable, the MRI must be obtained at baseline and at all subsequent response evaluations). If MRI is required for any other reason, this must first be discussed with the study medical monitor.

#### 7.1.3.3. Bone Marrow Aspirate And Biopsy

Bone marrow samples will be used for minimal residual disease assessment, to confirm cytopenic progression and distinguish autoimmune and treatment-related cytopenias.

##### *For Screening*

A unilateral bone marrow aspirate or biopsy must be obtained at Screening or up to 90 days prior to randomization.

##### *For Response Evaluation*

If the subject's physical examination findings, laboratory evaluations, and radiographic evaluations suggest that CR has been achieved in all response parameters, a bone marrow aspirate and biopsy must be obtained to confirm the CR and to evaluate minimal residual disease

(MRD). In cases where cytopenic progression is suspected, a bone marrow aspirate or biopsy should be performed to distinguish autoimmune and drug-related cytopenias.

#### ***For Evaluation of Clonal Evolution***

A bone marrow sample should also be collected at the time of disease progression for examination of clonal evolution (acquisition of new cytogenetic abnormalities defined as new del 11q, del 17p, or trisomy 12 by FISH, or other cytogenetic abnormalities).

***For Assessment of Minimal Residual Disease (MRD)*** A peripheral blood and bone marrow aspirate will be collected from all subjects at Cycle 9 and in those with a suspected CR after the start of study treatment, for assessment of MRD status.

- All responders who have an MRD-negative status in the bone marrow, should be followed with peripheral blood MRD assessments every 4 cycles until Cycle 33 then every 6 cycles starting at Cycle 39.
- All responders who have an MRD-positive status in the bone marrow or peripheral blood, should also be followed with peripheral blood MRD assessments every 4 cycles until Cycle 33 then every 6 cycles starting at Cycle 39. Once the subject becomes MRD-negative in the peripheral blood, this result should be subsequently confirmed with a bone marrow MRD assessment.
- A bone marrow aspirate will not be required at Cycle 9 for subjects who have unequivocal evidence of ongoing gross clinically detectable disease (eg, lymph node >2 cm), however these subjects should have a peripheral blood sample sent for MRD analysis and a bone marrow aspirate should be considered for the next scheduled response assessment visit.

The following material will be sent to the central laboratory:

- Bone marrow trephine ( $\geq 1$  cm) in a container of neutral buffered formalin (no other fixative allowed);
- Bone marrow aspirate
- Peripheral blood for MRD analysis.

#### **7.1.3.4. Cytogenetics: FISH / TP53 Assays**

Cytogenetic profiles will use FISH probes to detect abnormalities in chromosomes 13q, 12, 11q, and 17p. TP53 mutational status will be measured. For subjects with unknown del 17p or del 11q or TP53 status, a peripheral blood or bone marrow sample (aspirate or biopsy) must be tested, in accordance with institutional policies and procedures within 180 days prior to randomization. For subjects without lymphocytosis at Screening, FISH and/or TP53 assessment should be performed on the bone marrow sample.

Existing FISH and TP53 results performed within the last 180 days prior to randomization, confirming the status of del 17p, del 11q and TP53 as per the assay specification will be

considered adequate for eligibility and stratification purposes, provided appropriate documentation is available.

For all subjects, screening peripheral blood (required) and marrow samples (where available) will be sent to the designated central laboratory to be tested for 17p-, 13q-, +12, and 11q-.

#### **7.1.3.5. Genetic and Molecular Prognostic Markers**

A blood sample will be collected from all subjects during Screening and analyzed centrally to examine pretreatment prognostic factors.

These will include immunoglobulin heavy-chain variable (IgVH) and other genes known to be involved in CLL prognosis (eg, TP53, and Notch 1, SF3B1) mutational status.

In addition, genomic profiling of the tumor cells may be performed at baseline, during treatment or at progression as needed.

#### **7.1.4. Pharmacokinetics/Biomarkers**

##### **7.1.4.1. Sparse Pharmacokinetics**

Sparse PK samples will be collected in all subjects randomized to receive ibrutinib. The samples will be collected per subject as described below:

Cycle 1, Day 15:

1. Pre-dose
2. 1 hour (window: 45–75 minutes)
3. 2 hours (window: 1.5–2.5 hours)
4. 4 hours (window: 3.5–4.5 hours)

Cycle 2, Day 1:

1. Pre-dose (30-60 minutes before the dose)

Refer to the laboratory manual for instructions on collecting and processing these samples. On the day of the sampling visit, the clinical staff will instruct the subject to not take a dose before arrival at the clinic. Study drug intake will be observed by clinic staff. The actual time (versus requested time) that each sample is drawn must be recorded using a 24-hour format. The same clock should be used for recording the time of dosing. In the event that medical management (use of steroids) is needed, use of steroids for infusion should be recorded.

#### **7.1.4.2. Biomarker Assays**

Identification of signaling pathways or biomarkers that predict sensitivity or resistance to ibrutinib will be explored in this study.

For all subjects a predose blood sample will be collected at the specified visits per the Schedule of Assessments (Appendix A). If a subject progresses and returns to clinic within 24 hours after his or her last dose of ibrutinib, then an additional post-progression blood sample will be collected. If this post-progression blood sample is collected, then the biomarker blood sample collection at the EOT Visit is not required.

Samples collected may be used for pharmacodynamic and biomarker assessments including BTK and other kinase activity and signaling, expression analysis, sequencing, flow cytometry and secreted protein analyses. Fluids including blood collected during the course of the study may be used for, but not limited to, pharmacodynamic, biomarker and pharmacogenomic assessments.

A portion of pre-treatment bone marrow samples collected may be used by Sponsor for further biomarker analysis.

#### **7.1.4.3. Flow Cytometry-based Whole Blood Assays**

To explore and determine the temporal effect of drug combinations on the phenotype of the tumor cells and the immune system, blood samples will be collected on Day 1 of Cycle 1 (baseline), and at the intervals indicated in Section 8. Samples will also be collected at a suspected CR and at disease progression or discontinuation of treatment. Possible analyses will include but not limited to the staining for subpopulations of T, B, and NK cells.

#### **7.1.4.4. Cytokine and Chemokine Levels during Infusion of Obinutuzumab**

To explore and evaluate the impact of ibrutinib/chlorambucil on obinutuzumab-related infusion reactions, plasma will be collected at pre-dose ibrutinib/chlorambucil, immediately prior to infusion of obinutuzumab, and 2 and 4 hours into the obinutuzumab infusion for a total of 4 time points on Day 1. The samples will be evaluated for secreted proteins related to infusion reactions, such as IL-6, TNF-alpha, as well as other cytokines and chemokines.

### **7.2. Main Efficacy Evaluations**

Disease evaluations will include:

- Physical examination (which will focus on the presence/absence of size increase/ decrease in lymph nodes, liver, and spleen)
- Hematologic parameters by CBC performed at a central laboratory
- Radiographic evaluation (CT or MRI scan of the neck, chest, abdomen, and pelvis)

- Bone marrow aspirate and/or biopsy at Cycle 9 and as appropriate if there is evidence of CR in the other response parameters.
- MRD evaluation for subjects as described in Section 7.1.3.3.

If study drug is held before a scheduled response assessment then the response assessment can be delayed up to 4 weeks to allow re-initiation of study drug for 2 weeks (or as long as possible) prior to performing scheduled response assessment.

Efficacy assessments, for the purpose of the study result analyses, will be performed by an IRC blinded to study treatment information and independent of Investigators and personnel who are involved in the conduct of the study. The process and convention of the IRC will be detailed in a separate charter.

### **7.2.1. Definitions**

#### **7.2.1.1. Refractory**

Refractory is defined as treatment failure or progression within 12 months post-treatment.

#### **7.2.1.2. Relapsed**

Relapsed is defined as a subject who met criteria for CR or PR, but progressed beyond 12 months post-treatment.

#### **7.2.1.3. Treatment Failure**

Treatment failure is defined as best response of progressive disease or SD while on study treatment.

#### **7.2.1.4. Measurable Disease**

Subjects must have at least 1 measurable site of disease to participate in this study. Measurable sites of disease are defined as lymph nodes, or lymph node masses. Each measurable site of disease must be greater than 1.5 cm in the longest diameter. Measurement must be determined by imaging evaluation.

Tumor lesions that are situated in a previously irradiated area might or might not be considered measurable. If there are tumor lesions in previously irradiated areas and progression has occurred, these lesions will be considered measurable. If tumor lesions in previously irradiated areas are present and have been stable, then these lesions are not considered measurable. If tumor lesions in previously irradiated areas progress during the study, then disease progression will be considered as having occurred provided progression is confirmed by IRC.

All other sites of disease will be considered assessable. Assessable disease includes objective evidence of disease that is identified by radiological imaging, physical examination, or other procedures, as necessary, including peripheral blood counts.

### **7.2.1.5. Treatment-related Lymphocytosis**

Treatment-related lymphocytosis, for the purposes of this protocol, is defined as an elevation in blood lymphocyte count of  $\geq 50\%$  compared to baseline and  $\geq 5000/\mu\text{L}$  that occurs in the setting of unequivocal improvement in at least one other disease-related parameter including lymph node size, spleen size, hematologic parameters (Hgb or platelet count), or disease-related symptoms. Given the known mechanism of action of BCR-inhibiting agents including ibrutinib, treatment-related lymphocytosis is an expected and frequent pharmacodynamic phenomenon observed with initiation (or re-initiation) of ibrutinib.

Response assessment in CLL subjects treated with novel agents has been clarified by the authors of the IWCLL 2008 guidelines and is outlined in the NCCN NHL 2012 guidelines, supporting that subjects with isolated lymphocytosis in the setting of improvement in other disease parameters should not be considered to have progressive disease or treatment failure (Cheson 2012).

### **7.2.1.6. Richter's Transformation**

Richter's syndrome (RS) is lymphomatous transformation to a more aggressive histology in a subject with CLL or SLL. RS is most often characterized by the development of high-grade NHL or Hodgkin's disease. Symptoms of Richter's transformation can include new or progressive lymphadenopathy or organomegaly, fever, loss of weight and muscle mass, and other health problems. Richter's transformation can be suggested by a CT/PET scan, but should be confirmed with a biopsy (eg, lymph node) demonstrating the histologic transformation.

### **7.2.1.7. Minimal Residual Disease (MRD)**

Subjects who have achieved a CR/CRi should be evaluated for eradication of disease cells as determined on both peripheral blood and bone marrow aspiration. Subjects with a PR/nPR should be evaluated for MRD using a peripheral blood sample (or a bone marrow aspirate if possible) once MRD is confirmed negative in the peripheral blood a bone marrow aspirate must be sent to confirm MRD negativity at next clinical assessment. MRD negativity is defined as  $<1$  CLL cell per 10,000 leukocytes.

### **7.2.2. Guidelines for Disease Evaluation**

Table 5 outlines what is required for each parameter at baseline to be evaluable throughout the study.

**Table 5:      Evaluable Parameter Requirements**

Parameter	Requirements to be Evaluable for Response
Measurable Disease (required for all subjects)	Lymph Node > 1.5cm
Splenomegaly	Enlarged spleen
Hepatomegaly	Enlarged liver
Absolute Lymphocyte Count (ALC)	≥ 4,000 / $\mu$ L
Platelets	≤100,000 / $\mu$ L
Absolute Neutrophil Count (ANC)	≤ 1500 / $\mu$ L
Hgb	≤ 11.0 g/dL

**7.2.3. Response Categories**

Assessment of response should include physical examination, radiographic imaging, and evaluation of blood and marrow (if applicable). Definition of response for CR, CRi, nPR, PR, and disease progression will be evaluated by the criteria listed in Table 6. Group A criteria define the tumor load and Group B criteria define the function of the hematopoietic system. Response must be confirmed by CT and central labs, and must last at least 2 months without transfusional support or growth factor product to be considered a confirmed response.

**Table 6: Criteria for Response Categories**

Parameter	CR	PR	PD
Group A			
Lymphadenopathy a	None; ≤1.5cm	Decrease ≥50%	increase ≥50%
Hepatomegaly	None	Decrease ≥50%	increase ≥50% or new hepatomegaly
Splenomegaly	None	Decrease ≥50%	increase ≥50% or new splenomegaly
Blood lymphocytes	<4000/μL	Decrease ≥50% from baseline	increase ≥50% over baseline c
Marrow b	Normocellular, <30% lymphocytes, no B lymphoid nodules. Hypocellular defines CRi		
Group B			
Platelet count	>100,000/μL	>100,000/μL or increase ≥50% over baseline	Decrease of ≥50% from baseline secondary to CLL
Hemoglobin	>11 g/dL	>11g/dL or increase ≥50% over baseline	Decrease of >2g/dL from baseline secondary to CLL
Neutrophils	>1500/μL	>1500/μL or increase ≥50% over baseline	N/A

a Sum of the products of multiple lymph nodes (as evaluated by CT scans) or the longest diameter of one target lymph node

b This parameter is not relevant for the PD category unless confirming cytopenic progression.

c Subjects with treatment-related lymphocytosis should remain on study treatment in the absence of other criteria for progressive disease (see Section 7.2.1.5). For subjects without treatment-related lymphocytosis, PD by lymphocyte count can be considered based on ≥50% increase from the nadir count if confirmed by central lab on ≥2 serial assessments if the ALC is ≥30,000/μL and lymphocyte doubling time is rapid.

Note: Group A defines the tumor load and Group B defines the function of the hematopoietic system

**CR:** all of the criteria need to be met and subjects have to lack disease related constitutional symptoms. Bone marrow and aspirate is required to confirm CR.

**PR:** At least two of the Group A parameters must be met; with two exceptions: 1) subjects who only have abnormal lymph nodes at baseline, or 2) subjects who have only abnormal lymph node and abnormal lymphocyte count (ALC) at baseline. For these two exceptions, subjects will only need to meet the lymph node response criteria.

In addition to the Group A criteria, all subjects must also have a response in at least one of the Group B criteria.

**SD:** the absence of PD and the failure to achieve a response.

**PD:** at least 1 of the above criteria from Group A or B are met or development of transformation to a more aggressive histology

Cross reference: Hallek 2008, Hallek et al. June 2012 e-letter, Hallek 2013

### 7.2.3.1. Complete Response (CR)

All of the following are required for a CR:

- No significant lymphadenopathy (>1.5cm) palpable on examination or by CT
- No hepatosplenomegaly on examination or by CT
- No constitutional symptoms (ie, no fever >38°C for ≥2 weeks, no unintentional ≥10% body weight loss within last 6 months, no night sweats for >1 month without other evidence of infection, no fatigue interfering with work or usual activities)
- Neutrophils >1.5 x10^9/L, platelets >100,000/μL, and Hgb >11g/dL without recent growth factor or transfusions
- ALC <4,000 /μL

Marrow aspirate and biopsy must be performed by local lab after all other criteria meet the definition of CR. To define a CR, the marrow sample should be at least normocellular for age, with less than 30% of nucleated cells being lymphocytes. B-lymphoid nodules should be absent. In addition, in subjects with a CR, MRD should be performed on both peripheral blood and bone marrow aspirate to evaluate MRD status.

### 7.2.3.2. Complete Response with an Incomplete Marrow Recovery (CRi)

CRi is defined as a CR with an incomplete recovery of the subject's bone marrow. Subjects who have a CRi fulfill all criteria for a CR, but continue to have persistent anemia, thrombocytopenia, or neutropenia. These cytopenias are due to drug toxicity in the bone marrow and are not due to any evidence of CLL.

### 7.2.3.3. Nodular Partial Response (nPR)

nPR is a response where subjects meet criteria for a CR, but the bone marrow biopsy shows that there are still B-lymphoid nodules, which may represent a clonal infiltrate. These nodules are residual disease and therefore the subject is termed an nPR.

### 7.2.3.4. Partial Response (PR)

At least two of the following parameters must be met; with two exceptions: 1) subjects who only have abnormal lymph nodes at baseline, or 2) subjects who have only abnormal lymph node and abnormal lymphocyte count (ALC) at baseline. For these two exceptions, subjects will only need to meet the lymph node response criteria.

- ≥50% decrease in the sum products of up to 6 lymph nodes, a ≥50% decrease in the longest diameter of the single lymph node, or normalization of lymphadenopathy when compared to baseline.

- With no new enlarged lymph nodes by physical examination or CT AND no increase in any lymph node by CT. Note: In a small lymph node <2 cm, an increase of less than 25% is not considered to be significant.
- When abnormal, a  $\geq 50\%$  decrease in the enlargement of the spleen and/or liver from baseline or normalization by CT
- If abnormal a  $\geq 50\%$  drop in lymphocyte count from baseline or  $\leq 4.0 \times 10^9/L$

In addition to the criteria above, the subject must also have a response in at least one of the following evaluable criteria independent of growth factor support or transfusion.

- Neutrophils  $>1.5 \times 10^9/L$  or  $\geq 50\%$  improvement over baseline
- Platelets  $>100,000/\mu L$  or  $\geq 50\%$  improvement over baseline
- Hgb  $>11$  g/dL or  $\geq 50\%$  improvement over baseline

\* Note: If all criteria are normal, defined as neutrophils  $>1.5 \times 10^9/L$ , platelets  $>100,000/\mu L$ , and Hgb  $>11$  g/dL at baseline, they must remain normal to be considered consistent with a PR.

#### **7.2.3.5. Stable Disease (SD)**

Not meeting criteria for CR, CRi, nPR, PR, or progressive disease.

#### **7.2.3.6. Progressive Disease**

A CT scan is required to evaluate all cases of suspected progressive disease for this protocol regardless of the modality of disease progression (eg, lymph node, lymphocytosis, or transformation). Progressive disease requires at least ONE of following:

- New enlarged nodes  $>1.5$ cm, new hepatomegaly or splenomegaly; or other organ infiltrates
- $\geq 50\%$  increase from nadir in existing lymph node (must reach  $>1.5$  cm in the longest diameter) or  $\geq 50\%$  increase from nadir in sum of product of diameters of multiple nodes
- $\geq 50\%$  increase from nadir in enlargement of liver or spleen
- $\geq 50\%$  increase from the nadir count if confirmed by central lab on  $\geq 2$  serial assessments if the ALC is  $\geq 30,000/\mu L$  and lymphocyte doubling time is rapid, unless considered treatment related lymphocytosis (Section 7.2.1.5)
- New cytopenia (Hgb or platelets) attributable to CLL. The progression of any cytopenia (unrelated to autoimmune cytopenia, drugs, or bleeding), as documented by a decrease of Hgb levels from baseline by more than 20 g/L (2 g/dL) or to less than 100 g/L (10 g/dL) and lower than baseline, or by a decrease of platelet counts from baseline by  $\geq 50\%$  or to less than  $100 \times 10^9/L$  ( $100,000/\mu L$ ) and lower than baseline in the presence of active CLL, defines disease progression ; a marrow biopsy must demonstrate an infiltrate of clonal CLL cells if no other evidence of disease progression is present on CT scan.
- Transformation to a more aggressive histology (eg, Richter's Transformation). Whenever possible, this diagnosis should be established by biopsy.

Suspected progressive disease must be confirmed by a serial exam at least 2 weeks later. Please see Section 7.2.6 on details regarding suspected PD and IRC confirmation.

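### The sum-of-products limb of nodal progression carries no minimum node size, so nodes still within the complete-response limit can count as progression for the primary endpoint

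*Protocol*

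**What the plan says.** Protocol Section 7.2.3.6 lists the progression criteria under the rule "Progressive disease requires at least ONE of following". Three of them concern nodes:

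- **New nodes:** the criterion opens "New enlarged nodes" and requires more than 1.5 cm.
- **A single existing node:** a rise of at least 50% from nadir, with the added condition "must reach $>1.5$ cm in the longest diameter".
- **Several nodes:** a rise of at least 50%, worded "increase from nadir in sum of product of diameters of multiple nodes". No size condition and no minimum absolute increase follow.

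Table 6 gives only a 50% increase in its progression column. Its footnote a defines the nodal measure as "Sum of the products of multiple lymph nodes (as evaluated by CT scans", or the longest diameter when one target node is followed, again without a floor.

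Two neighbouring rules treat small nodes differently. For complete response, Section 7.2.3.1 requires "No significant lymphadenopathy (>1.5cm) palpable on examination or by CT", so nodes up to 1.5 cm are acceptable. In the partial-response definition, Section 7.2.3.4 says of nodes under 2 cm that "an increase of less than 25% is not considered to be significant". Section 7.2.5 follows up to six target nodes, each above 1.5 cm at selection, and gives no rule for those that later shrink below that size.

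IRC-assessed progression is a PFS event (Protocol Section 10.7.1; SAP Table 1). SAP Section 1.1 says that the response criteria are also detailed in an IRC charter, which is not among the documents.

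**The concern.** The three nodal criteria do not agree with each other or with the complete-response limit. One node growing from 10 to 15 mm, a 50% rise in diameter, is not progression because it does not exceed 1.5 cm. Two nodes growing from 10 x 8 mm to 12 x 10 mm are progression. A single scan can satisfy both the complete-response nodal limit and the progression criterion.

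Target nodes start above 1.5 cm and are expected to shrink on treatment, so the nadir sum can become small. A percentage rule on a small sum responds to changes of 2-3 mm. What is at stake is whether some primary-endpoint events reflect measurement variation, or growth that the rest of Section 7.2.3 does not regard as lymphadenopathy.

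**Working it through.** **Plan's own figure.** Inputs from Protocol Section 10.3 and SAP Section 1.4: HR 0.55, 1:1 allocation, two-sided 5%, 80% power. Freedman: (1.960 + 0.842)² x (1.55/0.45)² = 7.85 x 11.86 = 93.1, so 94 events. This matches the plan, with power of 80.4% at 94 events. Schoenfeld gives 88 events, and 82.6% power at 94. The sample size is not affected by this point.

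**Growth needed.** If every diameter grows by a factor k, the sum of products grows by k².

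- k² = 1.5 gives k = √1.5 = 1.225, or 22.5% per diameter.
- The largest nadir diameter that stays within 15 mm after such growth is 15/1.225 = 12.2 mm.

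**Examples with every node at or below 15 mm**

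| Nodes | Nadir | Later | Sum of products | Change |
|---|---|---|---|---|
| 2 | 10 x 8 mm | 12 x 10 mm | 160 to 240 mm² | +50% |
| 6 | 10 x 8 mm | 12 x 10 mm | 480 to 720 mm² | +50% |
| 6 | 9 x 7 mm | 11 x 9 mm | 378 to 594 mm² | +57% |
| 6 | 12 x 12 mm | 14.7 x 14.7 mm | 864 to 1,297 mm² | +50% |

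All four meet the sum-of-products limb and the complete-response nodal limit together. The 25% tolerance in Section 7.2.3.4 does not say whether it refers to diameter or area. Read as diameter, uniform growth of 22.5% is a change which that section calls not significant. Read as area, it is not.

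**Could chance alone do this?** The documents give no residual-size or measurement-error data, so the following are assumptions.

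*One comparison of two scans.* True size 10 x 8 mm and unchanged, independent error in each diameter. Probability of an apparent rise of 50% or more:

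| Nodes | SD 1.0 mm | SD 1.5 mm | SD 2.0 mm |
|---|---|---|---|
| 2 | 0.6% | 5.0% | 10.9% |
| 3 | 0.1% | 2.1% | 6.5% |
| 6 | <0.01% | 0.2% | 1.6% |

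*Whole schedule.* True longest diameters of 6-13 mm and unchanged, the eight scans at Cycles 5, 9, 13, 17, 21, 25, 29 and 33, a running nadir, and a confirming scan. The ranges below cover two implementations that differ in detail, such as the ratio of short to long axis. Share of subjects with a confirmed false progression:

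| Nodes | SD 1.0 mm | SD 1.5 mm |
|---|---|---|
| 2 | 4-6% | 26-29% |
| 3 | 1% | 11-14% |
| 6 | 0% | 1% |

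With two nodes and SD 0.5 mm the share is 0%. Requiring a node above 1.5 cm brings every setting to 1% or less.

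**The case against.** **The IRC charter may already contain a floor.** SAP Section 1.1 places the IRC's criteria there, and handling of shrunken target nodes is a usual charter topic. This stands as a limit on what can be concluded. It does not repair the protocol, which states the endpoint rule without a floor.

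**The text can be read as having a floor.** Table 6 equates nodes of 1.5 cm or less with no lymphadenopathy, and the other two nodal criteria carry the limit. That may well be the intent. But the condition in Section 7.2.3.6 stands before the alternative and attaches only to the single node, so the floor has to be inferred.

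**Confirmation protects the endpoint.** Sections 7.2.3.6 and 7.2.6 require a repeat evaluation at least two weeks later and IRC confirmation, and Section 7.2.5 asks for the same equipment and radiologist where possible. This reduces false events, and the whole-schedule model already includes a confirming scan. It does not affect small growth that persists below 1.5 cm.

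**Stronger readings that a reader might infer, and why they fail:**

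- *Six small nodes would often progress by chance.* Twelve diameters must rise together and stay up. That is concordant growth; noise gives 0-1%.
- *The trial loses power by a known amount.* If 2% of subjects in both arms had a false event, HR 0.55 would become 0.56 and power about 80%. At 5% in both arms it would be 0.58 and about 76%; at 5% in Arm A and 2% in Arm B, 0.60 and about 70%. Those shares are inserted values, and nothing in the documents supports them or the unequal split.
- *False progression leads directly to crossover.* Section 3.1 and Appendix A footnote d also require that the criteria for treatment are met.
- *A subject counted as a complete responder and as a PFS event is contradictory.* ORR uses best response, so any responder who later progresses is both. The inconsistency is only that one scan can meet both nodal criteria.

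**Conclusion.** The gap is real on the text. The sum-of-products limb lacks the 1.5 cm condition that the other two nodal criteria carry, and nodes of up to about 12.2 mm at nadir can meet it without leaving the complete-response range. That follows from the wording and simple geometry and needs no assumption.

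How often it would matter does rest on assumptions. Chance is a plausible cause mainly with two or three target nodes and an error SD of 1.0-1.5 mm. Such subjects are eligible, since Section 4.1 requires only one node above 1.5 cm. The documents give no distribution of node count, nadir size or measurement error, so the effect on the hazard ratio and on power cannot be computed. Any effect would probably be dilution toward 1, which would not create a false claim of benefit. This is a modest correction to a primary-endpoint definition and does not put the trial's conclusion in doubt.

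**What to change.** For IRC-assessed PFS, state that a rise of at least 50% from nadir in the sum of products counts as progression only if at least one contributing node exceeds 1.5 cm in longest diameter at that assessment. Put the same wording in Section 7.2.3.6, Table 6 and the IRC charter. If the charter already has this floor, bring the protocol into line with it. Settle this before the primary analysis.

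The cost is one clause. The downside is that some true early regrowth, with all nodes still at or below 1.5 cm, is dated at a later assessment; the rule is the same in both arms. The planned 94 events are unchanged. The proposal concerns how the endpoint is scored and makes no change to treatment or crossover rules.
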